
Data analysis
	
The primary efficacy variable is time to first occurrence of CV death, HF hospitalization or outpatient HF.
 
The secondary efficacy variables are:
 
 • Time to first occurrence of CV death or HF hospitalization • Time to first occurrence of HF hospitalization or outpatient HF (censoring will occur at the time of all-cause death) • Time to first occurrence of CV death, non-fatal spontaneous MI or non-fatal stroke • Cumulative number of events, including HF hospitalization, hospitalization due to non-fatal spontaneous MI, hospitalization due to non-fatal stroke and CV death. • Time to all-cause mortality 
Time-to-event is computed as the number of days from randomization to the start date of the endpoint event (first occurrence).
 
The primary endpoint will be analyzed using a Cox proportional hazards model stratified by STEMI/NSTEMI, with Treatment, PCI use at baseline and region included as factors in the model. The hazard ratio for LCZ696 vs. ramipril, the associated 2-sided 95% confidence interval and the 1-sided and 2-sided p-values will be presented from the analysis.
 
The primary endpoint and the first four secondary endpoints will be included in a hierarchical statistical testing strategy to control the familywise type I error rate at the 1-sided 2.5% level (in the strong sense).
 
Two interim analyses are planned to assess efficacy. The first interim analysis for efficacy is planned when approximately two-thirds of the target number of primary adjudicated events has been obtained. The second interim analysis for efficacy is planned to include primary events with onset date prior to 01-Mar-2020 (estimated start of COVID-19 impact globally). Sample size calculation: The sample size and power calculations described below are based on the study design prior to protocol amendment 4 when only one interim analysis had been planned. With the planned addition of a second efficacy interim analysis to include 80% of the target 708 primary events (see Section 9.7), there will be a small impact on power (approximately 0.1% power loss for the primary endpoint).
 
A sample size of 5,650 patients, randomized to LCZ696: ramipril using a 1:1 allocation ratio, has been chosen with the aim to obtain at least 708 first primary events and at least 592 first CV death or HF hospitalization events in this event-driven study. Seven hundred eight primary events will provide 80% power assuming a true Relative Risk Reduction (RRR) of 19% (i.e. a hazard ratio of 0.81) for LCZ696 vs. ramipril with statistical testing at the overall 2.5% 1-sided type I error rate (with strong control of the FWER). Five hundred ninety two first CV death or HF hospitalization events will provide 77.5% nominal power assuming a true RRR of 20% (for the intent-to-treat analysis) for this secondary endpoint for the same type I error rate. These calculations assume a 37 month recruitment period and approximately 4 month follow-up of the last randomized patient for endpoints to accrue in the field. An additional 1-2 months are expected through to the last patient last visit.


Key words
	
Spontaneous AMI, HF hospitalization, outpatient HF, LV systolic dysfunction, pulmonary congestion, STEMI, NSTEMI, randomized clinical trial, LCZ696, ramipril, echocardiography

1 Introduction

1.1 Background

Acute myocardial infarction (AMI) is one of the common reasons for cardiac hospitalization and its annual incidence in US, EU-5, Japan and China is currently estimated at 2.5 million per year. In the US alone, approximately 683,000 patients were discharged from hospitals in 2009 with a diagnosis of acute coronary syndrome (O’Gara, et al 2013). Although the community incidence rates for ST elevation myocardial infarction (STEMI) have declined over the past decade, those for non-ST-elevation myocardial infarction (NSTEMI) have increased. The overall incidence rate of AMI is expected to continuously increase in the next decades due to an ageing population and global rise in diabetes (Mozaffarian, et al 2015).

The in-hospital mortality of post-AMI patients has decreased in several parts of the world as a result of more frequent use of reperfusion strategies. Due to increasing numbers of post-AMI survivors, the prevalence of developing heart failure (HF), a frequent complication following an AMI, has increased worldwide (Jhund and McMurray 2009; Sulo, et al 2016). For example, of 63,853 patients discharged alive from their first AMI without a diagnosis of HF during 2001-2009 in The Cardiovascular Disease in Norway Registry (CVDNOR), 12.6% of patients developed HF during a median follow-up time of 3.2 years and nearly half of these cases occurred within 1 year from the index myocardial infarction (MI) discharge (Sulo, et al 2016). In addition, high-risk patients with left ventricular ejection fraction (LVEF) \leq 40% following an AMI representing approximately 1/4 to 1/3 of the overall post-AMI patient population, are known to have significantly greater risk of HF morbidity and mortality (Miller, et al 2012; van Diepen, et al 2015; Vasaiwala, et al 2012). In the VALIANT study of high-risk post-AMI patients (LVEF \leq 40% and/or transient HF signs with no prior history of chronic HF) who received percutaneous coronary intervention (PCI), approximately 20% of these patients experienced cardiovascular (CV) death or HF hospitalization over the approximate 2-year follow-up period (Pfeffer, et al 2003; Novartis data analyses on file). These real-world registry and controlled clinical trial data underscore the need for additional therapeutic approaches to reduce HF-related morbidity and mortality in post-AMI patients.

There are several mechanisms contributing to an unfavorable long-term prognosis in post-AMI patients. The most notable mechanism underlying the significantly greater risk of HF morbidity events following an AMI is pathological cardiac remodeling resulting from the loss of myocardium and maladaptive changes in the surviving myocardium. This remodeling process with changes in left ventricular (LV) geometry, size, and function is induced by altered myocardial loading conditions and dysregulated neurohumoral system (Pfeffer and Braunwald, et al 1990; Udelson and Konstam, et al 2002; White, et al 1987).

Factors triggering cardiac remodeling are activated within hours after an AMI. As supported by multiple clinical outcome studies conducted in the 1990s, early inhibition of the Renin Angiotensin System (RAS) with angiotensin converting enzyme (ACE) inhibitors has shown to reverse pathological remodeling, improve survival, and reduce HF hospitalization in post-AMI patients with LV systolic dysfunction and/or HF (AIRE Study Investigators, 1993; GISSI-12 Study Investigators, 1994; ISIS-12 Collaborative Group 1995; Kober, et al 1995;

Pfeffer et al 1992). As a consequence, guidelines recommend early initiation of ACE inhibitors after an AMI in patients with LV systolic dysfunction and/or HF for indefinite use (IA recommendation) (Anderson, et al 2007; Antman, et al 2008; Roffi, et al 2015; Steg, et al 2012). Despite this progress and a number of other evidence-based pharmacotherapies (β blockers, mineralocorticoid antagonists, etc.), the prognosis of high risk post-AMI patients with LV dysfunction and/or HF remains poor. Novel preventive strategies to reduce the risk for CV mortality and the clinical development of HF are clearly warranted.

Several lines of evidence have suggested that increasing natriuretic peptides in addition to RAS inhibition in post-AMI patients may offer greater benefits over the RAS inhibition alone. The potential mechanisms may include but are not limited to the anti-hypertrophic, anti-fibrotic, anti-ischemic, anti-inflammatory and sympatholytic effects of natriuretic peptides (Braunwald, 2015; D'Souza, et al 2004; Molkentin, 2003). In a small study of 24 anterior wall STEMI patients, the recombinant form of human BNP, nesiritide, given early after index MI presentation for 72 hours was well tolerated and associated with improved LVEF and reduced ventricular remodeling (i.e., smaller LV end-systolic volume) after 1 month (Chen, et al, 2009). A larger clinical study in Japanese STEMI patients (N=569) demonstrated that intravenous administration of atrial natriuretic peptide for 3 days after reperfusion treatment reduced infarct size and improved LVEF at 6-12 months (Kitakaze, et al 2007).

Entresto™ (sacubitril/valsartan, LCZ696) is a combination of neprilysin inhibitor and angiotensin II type 1 receptor blocker, providing concomitant neprilysin inhibition and angiotensin type 1 receptor blockade. Upon oral administration, LCZ696 delivers systemic exposure of sacubitril, a neprilysin inhibitor prodrug, and valsartan, an angiotensin receptor blocker (ARB). Sacubitril is then further metabolized by esterases to the active metabolite, sacubitrilat (LBQ657), which inhibits the degradation of natriuretic peptides and therefore enhances the effects of their biological activity. The efficacy and safety of LCZ696 titrated to a target dose of 200 mg twice daily in chronic HF patients with reduced ejection fraction (HFrEF) (LVEF \leq 40%) was evaluated in the PARADIGM-HF study (N=8,442) and demonstrated that LCZ696 significantly reduced the primary composite endpoint of CV death or HF hospitalization by 20%, as compared to enalapril (McMurray, et al 2014).

Given these positive results for the use of LCZ696 in the HFrEF patient population, and the improvement in LVEF, reduction in infarct size and ventricular remodeling observed in the STEMI patient population all of which suggest that increasing natriuretic peptides in addition to RAS inhibition may offer greater benefit in the post-AMI patient population, we hypothesize that early and sustained treatment with LCZ696 in high-risk patients with LV systolic dysfunction and/or pulmonary congestion following an AMI with no known prior history of chronic HF will be superior to the guideline recommended first-line treatment with ACE inhibitor as measured by a reduction in the composite endpoint of CV death, HF hospitalization or outpatient HF.

1.2 Purpose

The purpose of this study is to evaluate the efficacy and safety of LCZ696 titrated to a target dose of 200 mg twice daily, compared to ramipril titrated to a target dose of 5 mg twice daily, in addition to conventional post-AMI treatment, in reducing the occurrence of composite endpoint of CV death, HF hospitalization and outpatient HF (time-to-first event analysis) in

post-AMI patients with evidence of LV systolic dysfunction and/or pulmonary congestion, with no known prior history of chronic HF.

2 Study objectives and endpoints

2.1 Primary objective(s)

To demonstrate that LCZ696 is superior to ramipril in delaying the time-to-first occurrence of the composite endpoint of CV death, HF hospitalization or outpatient HF* in patients with LV systolic dysfunction and/or pulmonary congestion following an AMI

(*The outpatient HF endpoint event is defined as an adjudicated event of clinical development of symptomatic HF (either urgent/unscheduled or non-urgent) in the outpatient setting with symptoms and signs requiring initiation/intensification of intravenous or qualifying oral HF treatment. See [Section 6.4.1](#) for full definition)

2.2 Secondary objective(s)

- To demonstrate the superiority of LCZ696, compared to ramipril, in delaying the time-to-first occurrence of CV death or HF hospitalization
- To demonstrate the superiority of LCZ696, compared to ramipril, in delaying the time to new onset of symptomatic HF defined as time-to-first occurrence of HF hospitalization or outpatient HF
- To demonstrate the superiority of LCZ696 compared to ramipril, in delaying the time-to-first occurrence of CV death, non-fatal spontaneous MI or non-fatal stroke
- To demonstrate the superiority of LCZ696, compared to ramipril, in reducing the rate of the composite endpoint of CV death and total (first and recurrent) hospitalizations due to HF, non-fatal spontaneous MI or non-fatal stroke
- To demonstrate the superiority of LCZ696, compared to ramipril, in delaying the time to all-cause mortality
- To evaluate the safety and tolerability of LCZ696 compared to ramipril

(All secondary efficacy hypotheses except all-cause mortality will be included in a statistical testing strategy to control the familywise type I error rate) ([Section 9.5](#))

[REDACTED]

[figure not shown]
[REDACTED]

3 Investigational plan

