9.5.1 Efficacy variables

The secondary variables are defined as follows; the censoring mechanism will be the same as defined for the primary endpoint unless indicated otherwise:

- (1) Time from randomization to first occurrence of a confirmed composite of CV death or HF hospitalization
- (2) Time from randomization to first occurrence of a confirmed composite of HF hospitalization or outpatient HF (censoring will occur at the time of all-cause death)
- (3) Time from randomization to first occurrence of a confirmed composite of CV death, non-fatal spontaneous MI or non-fatal stroke
- (4) The cumulative number of composite events, including hospitalization due to HF, hospitalization due to non-fatal spontaneous MI, hospitalization due to non-fatal stroke and CV death. This endpoint is based on the total number of composite endpoints (count) and the patient-specific follow-up time from randomization to the last date the status of the patient was known (which could be the date of withdrawal from the study, the last visit prior to analysis cut off or the date of death).

(5) Time from randomization to all-cause mortality - patients without a death will be censored at the date of withdrawal from the study or the last day known to be alive (which may be established via telephone contact or the last visit prior to analysis cut off).

The secondary endpoints will be analyzed in order to compare LCZ696 vs ramipril using the ITT approach (i.e. estimation of the treatment effect under the ‘treatment policy’). Endpoints (1), (2), (3), and (5) will be analyzed using the same statistical analysis methods as specified for the primary analysis.

Secondary endpoint (4) will be analyzed using a negative binomial regression model with a Weibull baseline intensity function to allow flexibility if the baseline intensity is non-constant (Lawless, 1987). Treatment, STEMI/NSTEMI, PCI use at baseline and region will be included in the model as fixed effects. The relative rate ratio will be presented for LCZ696 vs ramipril together with 2-sided 95% confidence interval and 1-sided p-value.

Supportive analysis

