Endpoint (4), the total number of confirmed hospitalizations for HF, MI and stroke (including CV death) will be redefined for the patients who are prescribed open label Entresto™ as the total number of composite endpoints from randomization up to 28 days after the time of study treatment discontinuation. The analysis methods will remain the same as specified above.

Control of familywise type I error rate

The primary endpoint and the first four secondary efficacy endpoints will be included in a statistical testing strategy to control the familywise type I error rate at the 1-sided 2.5% level (in the strong sense). A hierarchical testing procedure will be employed whereby the primary hypothesis will be tested first, if rejected then the hypothesis associated with the first secondary endpoint will be tested and so on. The order of testing of the composite endpoints will be as follows:

- Primary endpoint
- Time to first CV death or HF hospitalization
- Time to first HF hospitalization or outpatient HF
- Time to first CV death, non-fatal spontaneous MI or non-fatal stroke
- The total number of composite events (hospitalizations (including CV death) due to HF, non-fatal spontaneous MI or non-fatal stroke and CV death).

[REDACTED]

[REDACTED]

[REDACTED]

[REDACTED]

[Redacted]

[Redacted]

[Redacted]

[Redacted]

[Redacted]

[Redacted]

[Redacted]

[Redacted]

[Redacted]

[Redacted]

[Redacted text block]

[Redacted text block]

[Redacted text block]

[Redacted text block]

[Redacted text block]

[Redacted text block]

[Redacted text block]

[Redacted text block]

[Redacted text block]

[Redacted text block]

[Redacted text block]

[Redacted text block]

[Redacted text block]

[Redacted text block]

[Redacted text block]

[REDACTED]

[REDACTED]

[REDACTED]

[REDACTED]

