9.7 Interim analyses

One interim analysis for efficacy was initially planned. The cut-off time for the first interim analysis was planned to be when about two-thirds of the target number of 708 primary events were reported and adjudication-confirmed. Approximately 472 of adjudication-confirmed primary events (i.e., first CV deaths, HF hospitalizations, or outpatient HF events) were planned; 464 adjudication-confirmed primary events were included. In the first interim analysis, the analysis dataset was comprised of all patients who were randomized before the cutoff date.

A second interim analysis for efficacy will be added in response to the potential impact from the COVID-19 pandemic, allowing the study to stop for overwhelming efficacy for the primary endpoint at one-sided alpha of 0.005. The second efficacy interim analysis will include all patients randomized prior to 01-Mar-2020 and all primary endpoint events that occurred prior to 01-Mar-2020, approximately 80% of the target 708 total primary endpoint events in the PARADISE-MI study. The data collected prior to 01-Mar-2020 are generally considered not impacted by the COVID-19 pandemic at the global level. Accordingly, patients who do not have a primary endpoint event prior to 01-Mar-2020 will be included in the second IA as censored.

Generalized Haybittle-Peto boundaries will be adopted for the interim statistical comparisons between treatments. An alpha of 0.001 (1-sided) was spent at the first interim analysis, and an alpha corresponding to the nominal level of 0.005 (1-sided) will be spent at the second interim analysis for the comparison of the primary endpoint. The rest of alpha (resulting in a nominal 1-sided 0.0244, with the currently specified target number of primary events of 708 and the planned addition of a second interim analysis to include 80% of the target 708 primary events, based on East version 6.4) will be used at the final analysis. The alpha to be spent for the final

[REDACTED]

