2.6.2 Statistical hypothesis, model, and method of analysis

The secondary endpoints will be analyzed in order to compare LCZ696 vs ramipril using the ITT approach (i.e. estimation of the treatment effect under the ‘treatment policy’).

Analysis of time to event variables

The time to event endpoints (1), (2), (3), (5) will be analyzed using the same statistical analysis methods as specified for the primary analysis. Treatment groups will be descriptively compared by presenting number and percentage of patients with events while inferential comparisons between treatment groups will be provided based on estimated hazard ratio and 95% CI. Both 1-sided and 2-sided p-values will be reported for treatment group comparison (LCZ696 vs. ramipril). Kaplan-Meier estimates of event rates will be tabulated for specific time points and will also be presented graphically.

Analysis of count variable

Secondary endpoint (4) will be analyzed using a negative binomial regression model with a Weibull baseline intensity function to allow flexibility if the baseline intensity is non-constant (Lawless, 1987). The regression model will consider the number of composite events as dependent variable with randomized treatment, STEMI/NSTEMI, PCI use at baseline and region as factors having fixed effects. Every event jump time, including the terminal event time, will be used to estimate the parameters specified in this model. For treatment group comparison LCZ696 vs ramipril, the relative rate ratio will be presented together with 2-sided 95% confidence interval and 1-sided and 2-sided p-values from the fitted model.

For descriptive summary, unadjusted annualized incidence rate will be provided along with the model-based estimates and their 95% confidence intervals will be presented by treatment groups. Also, adjusted event rate functions over time will be graphically presented from the estimated Weibull intensity.

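### All-cause mortality is stated as a superiority objective but sits outside the five-step testing sequence, so only a nominal result is possible even if all five tests reject

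*Protocol*

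**What the plan says.** Protocol 2.2 words the mortality objective like the other four secondary efficacy objectives: "To demonstrate the superiority of LCZ696, compared to ramipril, in delaying the time to all-cause mortality". The protocol summary and SAP Table 1-2 repeat it. Directly below the list, 2.2 states the exception: "All secondary efficacy hypotheses except all-cause mortality will be included in a statistical testing strategy to control the familywise type I error rate".

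Protocol 9.5.1 and SAP 2.6.3 carry this out. "The primary endpoint and the first four secondary efficacy endpoints will be included in a statistical testing strategy", in a fixed order: the primary; CV death or HF hospitalization; HF hospitalization or outpatient HF; CV death, non-fatal MI or non-fatal stroke; and the total-event composite. There is no sixth step.

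All-cause mortality is secondary endpoint (5) and has a planned analysis in the full analysis set: "Endpoints (1), (2), (3), and (5) will be analyzed using the same statistical analysis methods as specified for the primary analysis". SAP 2.6.2 adds a hazard ratio and 95% interval, and "Both 1-sided and 2-sided p-values will be reported for treatment group comparison".

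Protocol 9.7 and SAP 2.14 set the levels. "An alpha of 0.001 (1-sided) was spent at the first interim analysis", when "464 adjudication-confirmed primary events were included". The second interim uses a nominal 0.005 on "approximately 80% of the target 708 total primary endpoint events in the PARADISE-MI study". The final analysis has a nominal 0.0244. Both sections also say that, if the study continues, the secondary endpoints are tested at the primary's level. That sentence does not except endpoint (5).

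**The concern.** The wording of the objective and the inference behind it do not match. The objective promises a demonstration of superiority, yet the visible text gives this endpoint no alpha, success rule, power or nominal label. If the trial succeeded on every tested endpoint and mortality also favoured LCZ696, no familywise-error-controlled claim on mortality could follow.

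There is also a risk in the other direction. The level sentence in protocol 9.7 and SAP 2.14, read literally and apart from the hierarchy, could be taken to license a parallel mortality test at 0.0244. SAP 2.6.3 carries a note that the components of the primary are outside the sequence, but no such note for all-cause mortality.

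**Working it through.** **1. The level a sixth step would use.** Inputs (protocol 9.7): 464 events at the first interim (472 planned), 0.80 × 708 = 566.4 at the second, 708 at the end; one-sided nominal levels 0.001 and 0.005; overall 0.025. Under the null the three Z-statistics are jointly normal with correlation √(d_i/d_j), where d is the event count. Solving P(any boundary crossed) = 0.025 for the final level gives 0.02437 with 464 events and 0.02438 with 472. Both round to the plan's 0.0244.

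**2. The stated powers.** Inputs: protocol 9.8.2 and Table 9-6. Formula for 1:1 allocation: power = Φ(½√d·|ln HR| − z_α).

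| Step | Events | HR | One-sided α | Recomputed | Stated |
|---|---|---|---|---|---|
| Primary | 708 | 0.81 | 0.0249 | 80.0% | 80% |
| Secondary 1 | 592 | 0.80 | 0.025 | 77.5% | 77.5% |
| Secondary 2 | 566 | 0.83 | 0.025 | 60.1% | 60.1% |
| Secondary 3 | 594 | 0.85 | 0.025 | 50.8% | 50.8% |

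The 55.1% for secondary 4 (recurrent events) is taken as stated.

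**3. Does a sixth step cost anything?** It is tested only after five rejections, so it cannot alter any earlier test. For error control there are two cases:
- At least one of the first five nulls is true. A false rejection at step 6 then requires that true null to have been rejected already, so the familywise error has already been counted.
- All five are false. The only possible error is at step 6, at 0.0244.

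A simulation of the final analysis agrees (2,000,000 draws; assumed common correlation 0, 0.3, 0.5 and 0.7; first k hypotheses clearly false and the rest null, k = 0 to 5). The six-step familywise error was 0.024 to 0.025 throughout, and equal to the five-step rate whenever a null remained among the first five.

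**4. A parallel test outside the sequence.** Claiming on mortality at 0.0244 regardless of the sequence gives 1 − (1 − 0.0244)² = 0.048 under independence, a simulated 0.041 at an assumed correlation of 0.7, and at most 2 × 0.0244 = 0.0488.

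**5. Chance of reaching step 6.**
- Independent tests: 0.80 × 0.775 × 0.601 × 0.508 × 0.551 = 0.104.
- Upper bound: the smallest single power, 0.508.

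The endpoints share components, so the true value probably lies between. The secondary powers are nominal at 0.025, hence slightly optimistic against 0.0244.

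**6. Chance of also showing a mortality benefit.** The documents give no expected deaths, effect or power. For illustration only, assume 300 to 600 deaths at one-sided 0.0244. The formula in step 2 gives power of 48–78% at HR 0.80, 29–51% at 0.85 and 14–25% at 0.90. Under independence, multiplying the extremes by 0.104 gives 0.104 × 0.145 ≈ 1.5% to 0.104 × 0.777 ≈ 8%. Positive dependence would raise this.

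**The case against.** A sponsor may limit its confirmatory family, and this one did so openly. The exception stands next to the objective, and the protocol summary, protocol 9.5.1 and SAP 2.6.3 all follow it. The protocol and SAP do not conflict on this, and the error rate of the five tested endpoints is not threatened as long as the level sentence is read through the hierarchy. All of that stands.

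Mortality is also not neglected. CV death is a component of four of the five tested endpoints, it was part of the stopping rule at the first interim, and SAP 2.5.4 plans a version of the primary with all-cause death. This too stands, but none of it gives all-cause mortality a controlled test.

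A reader might infer that the mortality objective can never be met, or that the plan forbids testing it. The documents do not support that. Endpoint (5) has a pre-specified comparison with hazard ratio, interval and p-values, and no stated criterion bars reporting it. A reader might also take the 10% to 51% range as the chance of a mortality claim that is being given up. It is only the chance of reaching a sixth step.

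Low power for mortality is a fair reason not to expect success. It is not a reason against a last step that costs the others nothing.

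**Conclusion.** The point holds in a limited form: a superiority objective is paired with an analysis that can yield only a nominal result, although a controlled test was available without loss to steps 1 to 5. The practical gain from step 6 is modest and its size uncertain. The reach probability rests on the plan's assumed effects and on the unknown dependence between the tests, and the mortality figures rest on assumed deaths. The finding that step 6 is free rests on neither; it follows from the fixed sequence. Some analysis text is redacted and could not be checked, but the exception in protocol 2.2 is explicit.

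**What to change.** **Preferred:** by amendment before unblinding, add time to all-cause mortality as step 6, the last, in protocol 9.5.1 and SAP 2.6.3. Test it at the same alpha as the other secondary endpoints at whichever analysis applies (0.0244 at the final analysis as currently specified). Remove the exception in protocol 2.2 and align the protocol summary. Protocol Table 9-6 and SAP Table 3-6 cover the endpoints in the testing strategy, so a mortality row, with its assumed effect and expected deaths, belongs there too.

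**If the sponsor keeps mortality outside the sequence:** reword the objective to 'evaluate', label its p-value nominal, and limit the level sentence in protocol 9.7 and SAP 2.14 to the first four secondary endpoints.

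**Cost:** no alpha or power for steps 1 to 5 in either case. The edits are short, but a protocol change needs a formal amendment with ethics and, where required, health-authority approval (protocol 11.1). The first efficacy interim had already been run with CV death in its stopping rule. An amendment that adds a confirmatory mortality test should therefore give its reason and record that those deciding were blinded to the interim results.
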